3.3 Study Duration

The study is divided into 2 periods:

- Seven-day, single (subject)-masked vehicle run-in period
- Twenty-eight-day, active, double-masked treatment period commencing on Day 1, when the assigned treatment will be administered

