7.5.2 Baseline/Randomization Visit (Day 1)

Procedures should be conducted in the following order:

- Eligibility determination
- Medical/Ophthalmic history
- Concomitant medications
- Collect run-in vehicle/compliance assessment
- Urine pregnancy test (WOCBP only)
- Eye Dryness Score VAS
- Ocular Discomfort Score VAS
- Investigational product ASHRAE 7-point comfort VAS (pre-dose)
- Best-corrected VA OU
- Slit lamp biomicroscopy OU
- Corneal fluorescein staining OU
- First unanesthetized Schirmer's test OU (≥ 15 minutes post-CFS)
- Anesthetized Schirmer's test OU
- Intraocular pressure OU

- Randomization
- In-office IP administration OU (≥ 20 minutes post-CFS)
- Investigational product ASHRAE 7-point comfort VAS (5 ± 2 minutes post-dose)
- Symptom Assessment in Dry Eye questionnaire ($5 + 10$ minutes post-dose)
- Investigational product tolerability VAS ($5 + 10$ minutes post-dose)
- Investigational product ASHRAE 7-point comfort VAS (15 ± 2 minutes post-dose)
- Second unanesthetized Schirmer's test OU ($\geq 20 \pm 5$ minutes post-dose)Investigational product ASHRAE 7-point comfort VAS (30 ± 5 and 60 ± 5 minutes post-dose)
- Anesthetized Schirmer's test OU (post final Investigational Product ASHRAE 7-point comfort VAS)
- Dispense IP
- Adverse event assessment

7.5.3 Visit 3 (Day 8 ± 1 day), Visit 4 (Day 15 ± 2 days), and Visit 5 (Day 22 ± 2 days)

Procedures should be conducted in the following order:

- Concomitant medications
- Collect IP/compliance assessment/dispense IP
- Eye Dryness Score VAS
- Ocular Discomfort Score VAS
- Investigational product ASHRAE 7-point comfort VAS (pre-dose)
- Best-corrected VA OU
- Slit lamp biomicroscopy OU
- Corneal fluorescein staining OU
- Unanesthetized Schirmer's test OU (≥ 15 minutes post-CFS)
- In-office IP administration OU (≥ 20 minutes post-CFS)
- Investigational product ASHRAE 7-point comfort VAS (5 ± 2 minutes post-dose)
- Symptom Assessment in Dry Eye questionnaire ($5 + 10$ minutes post-dose)
- Investigational product tolerability VAS ($5 + 10$ minutes post-dose)
- Investigational product ASHRAE 7-point comfort VAS (15 ± 2 minutes post-dose)

- Investigational product ASHRAE 7-point comfort VAS (30 ±5 and 60 ±5 minutes post-dose)
- Adverse event assessment

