[h] Anesthetized Schirmer's to be performed after unanesthetized Schirmer's.

[i] Anesthetized Schirmer's to be performed post final IP ASHRAE 7-point comfort VAS. [j] IOP to be performed post anesthetized Schirmer's.

[k] Assignment of run-in IP (vehicle).

[l] IP administration must be performed at least 20 minutes after completion of CFS. Subjects should not dose IP at home the morning of Visits 2, 3, 4, 5, or 6.

[figure not shown]
[m] SANDE questionnaire and IP tolerability VAS to be performed between 5 and 15 minutes post-dose.

Representation of the IP Tolerability VAS. Subjects will grade the tolerability of IP after administration on a scale of 0 (no discomfort) to 100 (severe discomfort) by placing a vertical mark on the horizontal line. Study staff will measure and record the VAS.

Instructions: Please review the tolerability of the eyelid wipes. Rate how your eyes feel by drawing a single vertical mark through the horizontal line.

Representation of the IP ASHRAE 7-Point Comfort VAS. Subjects will rate the comfort of the eyelid wipes using the ASHRAE 7-point scale (-3 to +3) by placing a vertical mark on the horizontal line. Study staff will measure and record the VAS.

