Appendix 6 Symptom Assessment in Dry Eye Questionnaire

Subjects will grade their symptoms **over the past week** on a scale of 0 to 100 by placing a vertical mark on the horizontal line. Study staff will measure and record the VAS score.

SAnDE QUESTIONNAIRE

PLEASE COMPLETE THE FOLLOWING QUESTIONS REGARDING THE FREQUENCY AND SEVERITY OF YOUR DRY EYE SYMPTOMS.

Frequency of symptoms:

Place a vertical mark on the line to indicate how often, on average, your eyes feel **dry and/or irritated**:

Rarely All the time

Severity of symptoms:

Place a vertical mark on the line to indicate how severe, on average, you feel your symptoms of **dryness and/or irritation**:

Very Mild Very Severe

[figure not shown]

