- [e] Refraction at Visit 1 only unless ≥ 3 line reduction in VA.
- [f] Unanesthetized Schirmer's to be performed at least 15 minutes post-CFS.
- [g] Unanesthetized Schirmer's to be performed 20 ± 5 minutes post-IP administration.
- [h] Anesthetized Schirmer's to be performed after unanesthetized Schirmer's.
- [i] Anesthetized Schirmer's to be performed post final IP ASHRAE 7-point comfort VAS.
- [j] IOP to be performed post anesthetized Schirmer's.
- [k] Assignment of run-in IP (vehicle).
- [l] IP administration must be performed at least 20 minutes after completion of CFS. Subjects should not dose IP at home the morning of Visits 2, 3, 4, 5, or 6.
- [m] SAnDE questionnaire and IP tolerability VAS to be performed between 5 and 15 minutes post-dose.

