7. ANALYSIS OF ENDPOINTS

7.1. General Considerations

Summary statistics for the data collected during this study will be presented to give a general description of the subjects studied. Data from all sites will be combined in the computation of these descriptive summaries. Categorical variables will be summarized by the frequency and percentage of subjects in each category. Unless otherwise noted, the denominator to determine the percentage of subjects in each category will be based on the number of subjects with available data. When appropriate, comparisons on categorical data will be analyzed using the Cochran-Mantel-Haenszel or Fisher's exact test. Continuous variables will be summarized using N, mean, standard deviation (SD), median, minimum, and maximum values, and will be analyzed comparatively using the methodologies outlined under the primary and exploratory efficacy considerations (Sections 7.3 and 7.4) when appropriate.

For the descriptive statistics, minimum and maximum values will be calculated to the same number of decimal places as the source data. Means, medians and confidence limits will be calculated to one more decimal place than the source data. Standard deviations will be calculated to two more decimal places than the source data. Percentages will be calculated to the nearest one decimal place.

Unless otherwise specified or the parameter is evaluated OU, efficacy analyses will be performed on the SE only. Ocular safety summaries will be presented separately for the SE and the fellow eye (FE).

Efficacy variables will be summarized descriptively at each visit (where assessed) for both the SE and FE, and analyzed using appropriate statistical methods. The exam performed at Visit 2 (Day 1) will be used as baseline. If the assessment is missing or not evaluated on Day 1, the screening exam will be used, if available. Data from all clinical sites will be pooled so that the target sample size is available for analysis.

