7.4.1.4. SAnDE

A SAnDE evaluation will be conducted at each visit to measure dry eye symptoms from the week prior to the visit using the following scales, and measured using a similar methodology as identified in Section 7.2.3.5:

Frequency of symptoms:
Place a vertical mark on the line to indicate how often, on average, your eyes feel dry and/or irritated:

Rarely  All the time

Severity of symptoms:
Place a vertical mark on the line to indicate how severe, on average, you feel your symptoms of dryness and/or irritation:

Very Mild  Very Severe

The observed value and change from baseline for each subsequent post-baseline visit will be summarized descriptively by visit and treatment arm. Comparative analyses will be evaluated using the methodology outlined in Section 7.3.3.

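### The SANDE baseline is taken after the first randomised dose, so it is a value that treatment can affect

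*Protocol*

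**What the plan says.** Protocol 7.5.2 prescribes an order for Visit 2. The EDS and ODS scales and a first comfort rating come early, before any dose. Randomisation and in-office use of the assigned wipe follow, and only then the "Symptom Assessment in Dry Eye questionnaire". Note m to the schedule in Protocol Appendix 1 applies the same timing to every visit: "SANDE questionnaire and IP tolerability VAS to be performed between 5 and 15 minutes post-dose". Note m to SAP Table 1 repeats it: "SAnDE questionnaire and IP tolerability VAS to be performed between 5 and 15 minutes post-dose". Protocol 3.3 describes the second study period as "active, double-masked treatment period commencing on Day 1, when the assigned treatment will be administered", so the Visit 2 wipe is the first randomised dose.

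SAP 7.1 states: "The exam performed at Visit 2 (Day 1) will be used as baseline". It does not require a pre-dose value. Screening is only a fallback: "If the assessment is missing or not evaluated on Day 1, the screening exam will be used, if available". SAP 6.3 tabulates the Day 1 SANDE among the baseline variables.

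SAP 7.4.1.4 says: "A SAnDE evaluation will be conducted at each visit to measure dry eye symptoms from the week prior to the visit". It sends the comparison to the repeated-measures model of SAP 7.3.3, which analyses change from baseline with the baseline value as a covariate. Protocol Appendix 6 gives the recall period: "Subjects will grade their symptoms over the past week on a scale of 0 to 100".

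**The concern.** A baseline should be fixed before treatment can act on it. Here each active-arm subject rates SANDE minutes after a first exposure to a TRPM8 agonist. Each vehicle subject rates it after a product already used through the 7-day run-in. Any immediate difference between active and vehicle enters the baseline. It then passes into the change score, the model covariate and the baseline table.

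The plan treats its other symptom scales differently. EDS and ODS are completed before dosing at every visit, and the comfort VAS has a pre-dose reading. SANDE is the only symptom efficacy scale with no pre-dose value. The trial therefore cannot estimate a first-dose shift in SANDE or rule one out. At stake are the IVW-1001 versus vehicle contrasts in SANDE change at Weeks 1 to 4 (SAP 7.4.2), and a baseline table that could show an arm difference not present before treatment.

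**Working it through.** The documents give no SANDE effect size, SD or power, so there is no stated figure to reproduce. The check has two parts.

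**Order of events at Visit 2** (Protocol 7.5.2): EDS and ODS, then randomisation, then in-office dose, then SANDE at 5 to 15 minutes. No other SANDE is listed at that visit. Screening (Protocol 7.5.1) also places SANDE after an in-office wipe, but that wipe is vehicle in every subject and precedes randomisation.

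**Effect on the estimate.** SANDE runs from 0 to 100 and higher is worse, so count benefit as reduction. Define:
- D: true active-versus-vehicle benefit at a later visit.
- d: immediate active-versus-vehicle benefit in the Visit 2 rating (positive for relief, negative for discomfort).
- b: slope of the later score on baseline. The SAP 7.3.3 sample code has no baseline-by-visit term, so one slope serves all visits.

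On the benefit scale, let T be 1 for active and 0 for vehicle, let B0 be the rating without the first-dose shift, and let the recorded baseline be B = B0 + d*T. With the later score Y = a + b*B0 + D*T + error:
- Raw change: the contrast in Y - B is D - d, a bias of -d.
- Planned model: substituting B0 = B - d*T gives Y - B = a + (D - b*d)*T + (b - 1)*B + error. The treatment coefficient is D - b*d, a bias of -b*d.

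D, d and b are assumptions; none is in the documents. With D = 10:

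| d | raw change (10 - d) | model, b = 0.3 | model, b = 0.5 | model, b = 0.7 |
|---|---|---|---|---|
| 0 | 10 | 10 | 10 | 10 |
| 2 | 8 | 9.4 | 9.0 | 8.6 |
| 5 | 5 | 8.5 | 7.5 | 6.5 |
| -2 | 12 | 10.6 | 11.0 | 11.4 |
| -5 | 15 | 11.5 | 12.5 | 13.5 |

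A two-arm simulation (true effect 10, assumed SD 20, 400,000 subjects per arm) agrees with the formulas. At d = 5 the adjusted analysis kept 0.851, 0.748 and 0.652 of the effect for b = 0.3, 0.5 and 0.7, against 0.85, 0.75 and 0.65 by formula. Raw change kept about 0.50 in each case.

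**The case against.** The strongest objection is the recall period. At Visit 2 the past week is the vehicle run-in for all three arms, and nothing in the documents shows that one wipe moves a past-week rating within 15 minutes. That stands: d may be zero. It does not make the value pre-treatment, and a past-week question gains nothing from being asked after a wipe.

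A reader might infer that the change score does subtract part of the drug's effect. The documents do not support that. Both the existence and the sign of the shift are unknown. Protocol 1.5 names ocular discomfort as the primary potential risk, and immediate discomfort would inflate the apparent benefit.

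A reader might also infer that the Screening SANDE should simply replace Visit 2 as baseline. This is debatable. Suppose the shift is a passing sensation that colours the rating at every visit. With a past-week benefit of 10 and a recurring shift of 5, the Week 4 contrast is 15. Visit 2 raw change gives 15 - 5 = 10, the planned model gives 15 - 5b (13.5 at b = 0.3, 11.5 at b = 0.7), and a Screening baseline gives 15, the furthest from 10.

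Nor does the timing make SANDE unreadable beside EDS and ODS. Those ask about the present moment (Protocol Appendices 4 and 5), so the constructs differ already.

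One further defence is that every SANDE follows a dose, so like is compared with like. Consistent timing does not restore a baseline untouched by the assigned treatment.

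**Conclusion.** The point holds on timing and definition. The Visit 2 SANDE follows both randomisation and the first randomised dose, and the SAP uses it as baseline, change reference and covariate. No other provision in either document cures this.

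The size and direction of any bias are unknown. In the planned model it is -b*d, from zero if one dose leaves a past-week answer unmoved to a loss of 3.5 units in 10 at d = 5 and b = 0.7. Discomfort gives the same amounts with the opposite sign. These figures rest on assumed values of D, d and b.

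The reach is narrow. SANDE is one of many exploratory endpoints in a study whose primary objective the SAP calls safety. The primary Schirmer endpoint and the sample size do not depend on it. The change is worth making because it is cheap and the trial's own data cannot show whether the bias exists.

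**What to change.** **Protocol.** In 7.5.1 to 7.5.4, move SANDE into the pre-dose block with EDS and ODS at every visit. Limit note m, in both the protocol and the SAP, to the tolerability VAS, which has to follow a dose. The cost is reordering one short questionnaire. SAP 7.7 already describes the extent of missing efficacy data, so this may come too late for the present trial.

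**SAP, for data already collected.** In 6.3 and 7.4.1.4, label the Visit 2 SANDE as a post-first-dose value and do not tabulate it as a pre-treatment characteristic. Add a sensitivity analysis of Weeks 1 to 4 with the Screening SANDE as covariate and change reference. State its limits:
- It precedes the run-in, so change would include run-in response.
- Artificial tears could still have been in use in the week it recalls.
- Screening may be at any time of day, while later visits are held from 7 am to 12 pm.
- It does not remove post-dose colouring of the Week 1 to 4 ratings.

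The first three limits apply to all arms alike in expectation. The cost is a few SAP sentences and one extra model run.

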7.4.15 Intraocular Pressure

All IOP assessments must be measured by Goldmann applanation tonometry. The tonometer calibration should be checked for accuracy within 1 month before screening the first subject for the study with measurements recorded and filed before the first subject is screened; calibration must be checked monthly thereafter throughout the study. Variation within ± 2 mmHg is acceptable. The fluorescein and anesthetic agents should remain consistent throughout the study. Intraocular pressure will be measured following biomicroscopy and always prior to dilation.

Two consecutive IOP measurements should be taken, with the right eye measured first. The applanation probe should be withdrawn between measurements. If the first 2 measurements differ by >2 mmHg, a third measurement will be taken. Repeat for the left eye.

At the Screening Visit, Goldmann applanation tonometry must be performed after the completion of the unanesthetized Schirmer's test and prior to randomization to run-in IP.

At the Baseline Visit, Goldmann applanation tonometry must be performed after the completion of the unanesthetized Schirmer's test and prior to randomization to IP assignment.

At Visit 6, Goldmann applanation tonometry must be performed after the completion of the unanesthetized Schirmer's test.

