7.5.4 Visit 6/End of Study (Day 29 -3 to +1 days)

Procedures should be conducted in the following order:

- Concomitant medications
- Collect IP/compliance assessment/dispense IP
- Eye Dryness Score VAS
- Ocular Discomfort Score VAS
- Investigational product ASHRAE 7-point comfort VAS (pre-dose)
- Best-corrected VA OU
- Slit lamp biomicroscopy OU
- Corneal fluorescein staining OU
- First unanesthetized Schirmer's test OU (≥ 15 minutes post-CFS)
- In-office IP administration OU (≥ 20 minutes post-CFS)
- Investigational product ASHRAE 7-point comfort VAS (5 ±2 minutes post-dose)
- Symptom Assessment in Dry Eye questionnaire (5 +10 minutes post-dose)
- Investigational product tolerability VAS (5 +10 minutes post-dose)
- Investigational product ASHRAE 7-point comfort VAS (15 ±2 minutes post-dose)
- Second unanesthetized Schirmer's test OU ($\geq 20 \pm 5$ minutes post-dose)
- Investigational product ASHRAE 7-point comfort VAS (30 ±5 and 60 ±5 minutes post-dose)
- Anesthetized Schirmer's test OU (post final Investigational Product ASHRAE 7-point comfort VAS)
- Intraocular pressure OU to be performed post anesthetized Schirmer's
- Adverse event assessment

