Appendix 10 Anesthetized Schirmer's Test

Perform anesthetized Schirmer's Test after unanesthetized Schirmer's Test at Visit 2.

Perform anesthetized Schirmer's Test after the final IP ASHRAE 7-point comfort VAS (Visits 2 and 6).

Anesthetized Schirmer's test instructions:

- Instill proparacaine 0.5% drops bilaterally.
- Blot excess from ocular cul-de-sac and periorbital area; wait 5 minutes.
- While still inside the plastic sheath, fold the rounded end of the Schirmer's test strip at the first line on the strip (closest to the rounded end).
- Remove the right eye strip from the sheath.
- Ask the subject to look up and gently draw the right lower lid of the anesthetized eye in a downward and temporal direction.
- Place the rounded end of the strip toward the temporal one-third of the lower eyelid.
- Repeat this procedure in the left anesthetized eye.
- Darken the room.
- Instruct the subject to focus on the 20/400 E letter on the eye chart.
- Start the timer.
- Remove strips after 5 minutes.
- After removing the strips, place each strip on a flat surface beside a ruler.
- Visualize the leading edge and the lowest point of moisture and, using the ruler, measure a point halfway between the 2 points. Record this value as the amount of wetting.
- Retain Schirmer's test strips in source documentation for confirmatory measurement purposes.

Appendix 11

Sponsor Approval Signature

[figure not shown]
[figure not shown]
Study Title: Phase 1/2a, Proof-of-Concept, Multicenter, Parallel, Vehicle-Controlled, Double-Masked, Randomized Study Evaluating the Safety, Tolerability, and Efficacy of IVW-1001 Ophthalmic Eyelid Wipe in Subjects With Dry Eye Disease

Study Number: IVW-1001-CS-101

Version: 1.1

Final Date: 17 April 2024

This clinical study protocol has been approved by the Sponsor.

Appendix 12

Investigator's Signature

Study Title: Phase 1/2a, Proof-of-Concept, Multicenter, Parallel, Vehicle-Controlled, Double-Masked, Randomized Study Evaluating the Safety, Tolerability, and Efficacy of IVW-1001 Ophthalmic Eyelid Wipe in Subjects With Dry Eye Disease

Study Number: IVW-1001-CS-101

Version: 1.1

Final Date: 10 April 2024

By signing below, the Investigator agrees to adhere to the protocol as outlined and agrees that any changes to the protocol must be approved by IVIEW Therapeutics, Inc. prior to seeking approval from the Institutional Review Board.

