7.2.3.5. VAS of IP Tolerability

A VAS evaluation of the IP tolerability will be performed at all visits and the Day 1 value will be used as the baseline value. Subjects will grade the tolerability of the IP after administration on a scale of 0 (no discomfort) to 100 (severe discomfort) by placing a vertical mark on the horizontal line shown below. The mark will be measured and recorded.

The VAS will be measured at all visits and the Day 1 value will be used as the baseline value. The observed value and change from baseline for each subsequent post-baseline visit will be summarized descriptively by visit and treatment arm.

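### The Day 1 tolerability score is not a usable baseline: it follows both the first randomised dose and topical anesthetic, and no anesthetic precedes the dose at Visits 3 to 6

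*Protocol*

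**What the plan says.** **Order at Visit 2.** Protocol 7.5.2 fixes the sequence: "Procedures should be conducted in the following order". The relevant items run: first unanesthetized Schirmer's test, anesthetized Schirmer's test, intraocular pressure (IOP), randomisation, in-office dose, tolerability VAS, then "Second unanesthetized Schirmer's test OU". Appendix 10 agrees on the early anesthetized test: "Perform anesthetized Schirmer's Test after unanesthetized Schirmer's Test at Visit 2".

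**Anesthetic.** Appendix 10 directs the site to "Instill proparacaine 0.5% drops bilaterally", then "Blot excess from ocular cul-de-sac and periorbital area; wait 5 minutes". Protocol 7.4.15 requires Goldmann tonometry for every IOP reading, places it before randomisation at Visit 2, and treats anesthetic as part of the procedure: "The fluorescein and anesthetic agents should remain consistent throughout the study".

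**Later visits.** Visits 3 to 5 have neither an anesthetized Schirmer's test nor IOP (Protocol 7.5.3; SAP 7.2.3.2). At Visit 6 both close the examination sequence, with "Intraocular pressure OU to be performed post anesthetized Schirmer's" (Protocol 7.5.4).

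**Analysis.** For the tolerability VAS, SAP 7.2.3.5 states that "the Day 1 value will be used as the baseline value". It plans descriptive summaries, by visit and arm, of the observed score and of change from baseline. Protocol 9.5 likewise includes tolerability among the safety assessments shown as absolute values and changes.

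**The concern.** A baseline for a change score should be free of the randomised treatment and measured under the same conditions as the follow-up values. The Day 1 tolerability score fails on both counts. It rates the first randomised wipe, so any discomfort from active treatment is already in it. It is also taken after anesthetic drops, which the scores at Visits 3 to 6 are not.

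Tolerability is on the list of primary safety measures, and Protocol 1.5 names ocular discomfort as the main potential risk. The Appendix 2 instruction asks subjects how their eyes feel, so numbness of the ocular surface could bear on the answer even though the wipe is applied to the lid. A reader of the change table could conclude that active treatment adds no discomfort, or that tolerability deteriorates with use, when neither is so.

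**Working it through.** The plan gives no figure to reproduce. The check compares visit orders, adds the stated intervals, and works out what a change score would show.

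**1. Anesthetic before the dose, by visit**

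| Visit | Listed before the in-office dose | Source |
|---|---|---|
| 1 (Screening) | Tonometry | Protocol 7.5.1 |
| 2 (Day 1) | Anesthetized Schirmer's and tonometry | Protocol 7.5.2 |
| 3, 4, 5 | Neither | Protocol 7.5.3 |
| 6 | Neither (both come after all post-dose scores) | Protocol 7.5.4 |

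Corneal staining does not alter this table: the dye strip is wetted with saline or sterile water (Appendix 8). The mismatch is Visits 1 and 2 against Visits 3 to 6.

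**2. Elapsed time at Visit 2**

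Inputs: a 5-minute wait after the drops and a 5-minute strip test (Appendix 10); tolerability VAS 5 to 15 minutes post-dose (Appendix 1, note m); second unanesthetized Schirmer's 20 ± 5 minutes post-dose (note g), that is 15 to 25. Let g be the unstated time for IOP, randomisation and dosing.

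- Proparacaine to VAS: 5 + 5 + g + (5 to 15) = 15 to 25 minutes + g.
- Proparacaine to second Schirmer's: 5 + 5 + g + (15 to 25) = 25 to 35 minutes + g.
- With g assumed to be 0 to 5 minutes: 15 to 30 and 25 to 40 minutes.
- From a separate tonometry drop, if given, the intervals are shorter: 5 to 15 and 15 to 25 minutes, plus the unstated time from that drop to dosing.

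The rule that dosing must wait 20 minutes after staining adds no washout. By then 15 + 5 + 10 = 30 minutes have passed at the least (staining to first Schirmer's, that test, and the anesthetized test).

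Duration of anesthesia is not in the documents. Assume 10 to 30 minutes from proparacaine, with g at 0 to 5. At 10 minutes neither measure is touched. At 20 minutes the VAS can be, but the second Schirmer's is not. At 30 minutes the VAS falls wholly within it and the Schirmer's in part.

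**3. What the change score shows**

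Let vehicle score v and active score v + D at every visit when no anesthetic has been given. On Day 1 let anesthesia lower both arms by b and mask a further fraction m of D on active (m from 0 to 1).

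| | Day 1 | Visits 3 to 6 | Change |
|---|---|---|---|
| Vehicle | v − b | v | b |
| Active | v + D − b − mD | v + D | b + mD |
| Active minus vehicle | (1 − m)D | D | mD |

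- m = 0 (no differential masking): the difference in change is 0. A real and constant excess of D disappears.
- m = 1 (complete masking): the difference in change is D, and it reads as worsening over time.
- Between these, it is mD.
- A common effect b cancels between arms but appears as worsening of b within each arm.

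The observed difference at Visits 3 to 6 is D whatever m and b are. The m = 0 row needs no anesthetic effect at all; it follows from scoring baseline after the randomised dose.

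**The case against.** The strongest reply is that little turns on this. Three parts of it stand.

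- **Size.** The documents give no duration of anesthesia, and g is probably longer than 5 minutes: tonometry needs at least two readings per eye, followed by system assignment and a supervised first use. The drops go into the eye while the wipe goes on the lid. Differential masking is possible but not shown.
- **Reach.** The listed primary safety measure is the VAS itself; change from baseline is an added summary. No test of tolerability is planned, and observed scores by visit and arm are already in SAP 7.2.3.5.
- **Schirmer's.** No endpoint or estimand uses the post-dose test.

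It can also be said that change from the first dose describes adaptation with repeated use. That would be a fair purpose, but here it is confounded with the anesthetic that preceded only the first randomised dose.

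A reader might go further and infer that the primary endpoint is contaminated. The documents do not support this. SAP 7.3.1.1 ties the test to the interval after staining, which points to the first Visit 2 test, done before any anesthetic. It does not name the first test outright, but nothing selects the second. A reader might also infer that Day 1 is the only affected visit; tonometry also precedes the vehicle dose at Screening.

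None of this rescues Day 1 as a baseline, because the score still follows the first randomised dose.

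**Conclusion.** The point holds for the tolerability baseline. Change from Day 1 is a change neither from a pre-treatment value nor from a like-for-like one. Under a constant excess D on active, the between-arm difference in change lies anywhere from 0 to D, depending on a masking fraction that nobody measures, while observed scores at Visits 3 to 6 give D. This assumes a constant D and no floor or ceiling effect on the 0 to 100 scale. The size of any anesthetic effect cannot be derived from the documents.

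The weight is moderate: one descriptive safety summary could mislead, no planned test is affected, and the sound summary is already specified beside it.

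As a note only, the Visit 2 second unanesthetized Schirmer's test follows anesthetic and the Visit 6 one does not, so the two are not comparable and the Visit 2 value should not serve as a baseline.

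**What to change.** Keep the visit order and amend the SAP before database lock and unmasking, as SAP Section 1 allows.

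1. In SAP 7.2.3.5, remove Day 1 as baseline and remove the change-from-baseline summary for tolerability. Do not substitute Screening, where tonometry also precedes the vehicle dose.
2. Make observed scores by arm and visit the safety summary, with the comparison of arms resting on Visits 3 to 6.
3. Show Day 1 separately, with a footnote that anesthetic preceded the dose. The same footnote can cover the Day 1 SANDE and post-dose ASHRAE comfort scores, which share the timing.
4. Record the change in SAP 7.7, because Protocol 9.5 plans changes from baseline for tolerability.
5. State in SAP 7.3.1.1 that the first, pre-dose Visit 2 test is the Schirmer's baseline and that the second Visit 2 test is not used as one.

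The cost is SAP wording and table layout. The only loss is the change-from-baseline table for tolerability.
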